**Description of Intervention:**

- 1) All participants included in the study will receive daratumumab subcutaneous injection therapy (fixed dose 1800mg). On study, participants will receive 2 cycles of daratumumab in the infusion center, followed by 4 cycles at home followed by 2 more cycles at the infusion center. At the beginning of each cycle, patient reported outcome surveys and quality of life surveys will be collected (EORTC-QLQ-30, CTSQ, COST, and OOCAT). During the infusion center phase, administration will be given by an infusion center nurse. During the home infusion phase of the study a home infusion nurse will administer darzalex-faspro. During home administration, specific details on barriers to maintaining adherence will be collected and described with descriptive analysis (i.e. issues with storage, delivery, disposal of medication).

**Study Duration:** 36 months

**Participant Participation Duration:** 10 months

**Estimated Time to Complete Enrollment:** 26 months

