## **3 Study Design**

### **3.1 Characteristics**

Open label, non-randomized trial in patients with multiple myeloma who are receiving DARZALEX FASPRO (daratumumab and hyaluronidase).

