### 11.2 Analysis Plans

For primary analysis, the SWT domain CTSQ scores after all cycles will be analyzed jointly in a linear mixed effects model with a random effect of patient and the fixed effect of the delivery mode (home vs. infusion center). Log or other transformation of CTSQ scores will be used, as appropriate, to satisfy the model assumptions. Possible time trends will be considered in the model and incorporated, if significant. The mean difference in CTSQ scores between home and infusion center will be computed with the corresponding 95% confidence interval and tested (null hypothesis of zero mean difference) using appropriate model-based contrast with alpha 0.05.

The same approach will be used for the secondary analysis of other CTSQ domains, EORTC QLQ-30, COST survey, and OOCAT survey scores.

The adherence at the home setting cycles will be analyzed in repeated measures logistic regression model with a random effect of patient and the fixed effect of the delivery mode (home vs. infusion center). The model will be used to compute the average rate of home setting adherence with the corresponding 95% confidence interval.

---

Secondary endpoints related to the barriers to home administration and exploratory endpoints related to the patient perceptions of home based anti-neoplastic therapy will be summarized using descriptive statistics.

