### **11.4 Sample Size Considerations**

The model-based contrast to be used for testing the primary null hypothesis is a generalization of the paired t-test to the case of more than one observation under each delivery mode (scores for 4 cycles at infusion center and 4 cycles at home). The proposed sample size of 20 patients provides 80% power to detect the minimally important difference of 5.9 points (Usmani et al, 2020) for CTSQ SWT domain score using the two-sided paired t-test with alpha 0.05 and assuming that the standard deviation of within patient differences is at most 8.92. Based on between-patient standard deviation of 13.76 for CTSQ SWT domain scores reported in Trask et al (2008), the standard deviation of within patient differences will be 8.92 or lower if the correlation between repeated score from the same patient is 0.79 or higher. The actual power will be higher since multiple observations per each delivery mode will be utilized in the linear mixed effects model.

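### The primary contrast pools the center cycles before and after home, so the plan never checks whether scores return toward the C1-2 level when home delivery ends

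*Combined protocol and SAP*

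**What the plan says.** The Study Summary (Description of Intervention) fixes one order for everyone: "2 cycles of daratumumab in the infusion center, followed by 4 cycles at home followed by 2 more cycles at the infusion center". Section 3.1 describes an "Open label, non-randomized trial in patients with multiple myeloma", so there is no parallel group and no reversed order.

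Section 11.2 analyzes the CTSQ SWT scores from all cycles in "a linear mixed effects model with a random effect of patient and the fixed effect of the delivery mode (home vs. infusion center". One contrast is tested: "The mean difference in CTSQ scores between home and infusion center will be computed with the corresponding 95% confidence interval". Section 11.4 confirms that the center cycles count as one condition, with "scores for 4 cycles at infusion center and 4 cycles at home". On time, Section 11.2 adds only this: "Possible time trends will be considered in the model and incorporated, if significant". No form of trend is named. No term or contrast separates C1-2 from C7-8. The same approach is applied to the other CTSQ domains, EORTC, COST and OOCAT.

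**The concern.** With one group and one sequence, site of care is tied to calendar position. The return to the center at C7-8 is the design feature that can link a change to the site: if home delivery caused the change, scores should move back toward the C1-2 level. The planned model collects those cycles but merges them with C1-2.

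Three different histories can then give a positive home coefficient: a home benefit that reverses, a change around C3 that never reverses, and a fall that appears only when home delivery is withdrawn. Section 11.1 states a comparative hypothesis about site of care. A positive result could be read as supporting it even when C7-8 scores, back in the center, are as high as the home scores.

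**Working it through.** **Inputs.** From Section 11.4: 20 patients, two-sided alpha 0.05, minimally important difference 5.9, SD of within-patient differences 8.92, between-patient SD 13.76, correlation 0.79. Assumed here: equal correlation between all cycles, complete data, and correlation 0.5 as a less favorable case.

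**The plan's own figure.** Paired t-test, 19 df: 5.9 / (8.92/√20) = 5.9/1.995 = 2.96, which gives 80.1% power. SD check: 13.76 × √(2 × 0.21) = 8.92. Both reproduce, so the sample-size calculation is not in error.

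**What each pattern does to the contrasts.** The pooled center mean is the average of C1, C2, C7 and C8.

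| Pattern | Home minus pooled center | Home minus C1-2 | Home minus C7-8 |
|---|---|---|---|
| Reversible home effect s | s | s | s |
| Lasting shift s from C3 | s − (0+0+s+s)/4 = s/2 | s | 0 |
| Drop of s at C7-8 only | 0 − (0+0−s−s)/4 = s/2 | 0 | s |
| Home benefit s fully carried into C7-8 | s/2 | s | 0 |
| Linear drift b per cycle | 0 | 3b | −3b |

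**Other onsets of a lasting shift.** From C2: s − 3s/4 = s/4. From C4: 3s/4 − s/2 = s/4. From C5: s/2 − s/2 = 0. From C6: s/4 − s/2 = −s/4.

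**Does the time-trend sentence remove it?** The mean cycle number is 4.5 for home and 4.5 for the pooled center, so linear time is uncorrelated with mode. Projecting the C3 step on the model gives a mode coefficient of 0.50 with mode alone, 0.50 with linear time added, and 0.50 with linear plus quadratic time. A log-time term leaves 0.35. Cycle as a categorical factor cannot be fitted beside mode (rank 8 for 9 columns).

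**Size, for a lasting 5.9-point shift at C3 and no home effect.** The bias is 5.9/2 = 2.95.
- Correlation 0.79: residual SD 13.76 × √0.21 = 6.31; SE 6.31 × √((1/4+1/4)/20) = 0.997; 2.95/0.997 = 2.96; significant in 80% of trials.
- Correlation 0.5: residual SD 9.73; SE 1.54; 2.95/1.54 = 1.92; significant in 44%.
- If the per-patient pooled contrast itself had SD 8.92: 29%.

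The match with the plan's 80% follows from the arithmetic: the bias is half of 5.9, and averaging four cycles per mode halves the SE. Simulation at 0.79 (20,000 trials) agrees: mean estimate 2.94, significant in 80%. With a linear term added, the slope was significant in 97% of trials, yet the mode estimate stayed at 2.94 and was significant in 83%.

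**Precision of the separate contrasts.** SE = residual SD × √((1/4+1/2)/20), which is 1.22 at 0.79 and 1.88 at 0.5. With the 19-df multiplier 2.093, the 95% half-widths are 2.093 × 1.22 = 2.6 and 2.093 × 1.88 = 3.9 points.

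**The case against.** The strongest reply has four parts.

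- **The scenario is the least favorable one.** An abrupt, permanent shift of a full 5.9 points exactly at C3 is not described anywhere. Patients enter already on monthly daratumumab (Section 4.1.1). The premedication changes allowed in Section 5.7.1 fall at C3-C4 only if doses are counted from C1, and many patients may be past them. This stands: the 80% is an illustration, not a forecast.
- **The pooled contrast has a real virtue.** It cancels linear drift, which neither separate contrast does (3b and −3b above). This stands, and is the reason to keep it as the primary test.
- **Non-reversal is ambiguous.** Full carry-over of a home benefit and an unrelated lasting change give identical rows in the table. This also stands. Separate contrasts show that scores did not reverse, but not why. The pooled number hides even that.
- **This is a 20-patient pilot with an exit interview on home versus center.** The interview helps interpretation but does not repair the primary estimate.

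A reader might infer that a significant home minus C7-8 should be required before any claim. The figures do not support that gate. It cuts false claims under the C3 shift to about 2.5%. Under a 5.9-point drop at C7-8 only, however, it still claims a site effect in 80% (correlation 0.79) or 44% (0.5) of trials. For a true 5.9-point effect with a 1-point-per-cycle rise, home minus C7-8 has expectation 5.9 − 3 = 2.9, and power falls to about 61% or 30%. The pooled test keeps about 100% or 95%.

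**Conclusion.** The concern holds in limited form. Section 11.2 pools two center phases that the design needs kept apart, and no planned analysis shows whether scores moved back after home. Half of a lasting shift at C3 enters the home estimate, a quarter of one at C2 or C4 (with mode alone or with a linear term), and none at C5; half of a drop confined to C7-8 enters too. The linear and quadratic trend terms that the plan might add leave the C3 bias unchanged.

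The fractions rest only on the 2-4-2 layout and complete data. The 80% and 44% also rest on equal correlation between cycles and on a shift of 5.9 points.

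A reader might go further and infer that a positive primary result would probably be spurious, that the whole of a lasting shift is counted as a home effect, or that the analysis has no protection against time. The documents support none of these. They do not establish that a shift will occur, at most half of one enters, and linear drift is balanced by design.

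**What to change.** In Section 11.2, before analysis:

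1. Replace the two-level mode term with a three-level phase term: center before, home, center after.
2. Keep the planned primary test as home minus the equal-weight average of the two center phases. With complete data this is the same estimate.
3. Prespecify reporting of home minus C1-2 and home minus C7-8, each with a 95% confidence interval, for the primary score and for the other scores that use this model.
4. State that a site-of-care interpretation rests on both contrasts pointing toward home. If they disagree, report a change that did not reverse, or one that appeared only on return, and say that it may reflect carry-over or an unrelated lasting change.
5. Do not make significance of home minus C7-8 a condition.

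Read the intervals and not just the signs: under a lasting C3 shift, home minus C7-8 is centered on zero and will be positive by chance about half the time. Also say whether the time-trend sentence applies to this model. A linear term beside the three phases multiplies the SE of each separate contrast by √3 (1.22 × √3 = 2.11 at correlation 0.79).

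The cost is a few sentences and two extra contrasts from data already collected. The primary test and its power do not change. The separate contrasts are less precise than the pooled one, and home minus C7-8 depends on the last cycles, where withdrawals (Section 4.4.2) will be felt most.

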## Study Summary

Title:	Open Label Single Arm Study to Assess the Implementation of Home based daratumumab administration.
Précis:	This study will include all patients on the monthly phase of daratumumab. Patient reported outcome metrics as well as implantation metrics will be measured.
Objectives:	
Primary: Evaluate treatment burden (using the CTSQ).
 
Secondary:
 

1. Determine adherence to home delivery of Darzalex-Faspro.

2. Evaluate quality of life (using EORTC QLQ-30) based on site of care (home vs. infusion center).

3. Evaluate financial burden (using the COST survey) based on site of care (home vs. infusion center).

4. Evaluate Safety of home administration of darzalex-faspro.

5. Evaluate barriers to home administration.

 
Exploratory:
 

1. Evaluate patient perceptions of home administration of anti-neoplastic therapy

2. Evaluate opportunity cost based on site of care (home vs. infusion center) using the Oncology Opportunity Cost Assessment Tool (OOCAT)

Population:	The sample size will be 20 participants. All patients with a diagnosis of multiple myeloma who are receiving the monthly phase of daratumumab.
Phase:	Pilot study
Number of Sites:	1- Sidney Kimmel Cancer Center Thomas Jefferson University [name]

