### **2.2.2 Secondary**

1. Adherence is defined as completing administration of medication in the home setting. Adherence will be measured for each dose given and failure would occur if the participant needs to go to the infusion center for administration for whatever reason. Based on previous studies of home based administration adherence rates over 75% would be needed to meet criteria for feasibility.
2. Measurement of quality of life will be measured using the EORTC QLQ-30.
3. Financial toxicity will be measured using the COST survey.
4. Safety will be evaluated through collection of adverse events, administration reactions related to Darzalex-Faspro.
5. Barriers to home administration will be measured through any delays in treatment related to delivery of medication, arrival time of the infusion nurse, issues related to storage of medication, issues related to administration of the medication.

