### **4.4.2 Handling of Participant Withdrawals and Participant Discontinuation of Study Intervention**

Participants who withdraw or discontinue the study intervention early will continue to receive their treatment in the infusion center as per the standard of care. If a patient withdraws from study early, end of study visit (semi-structured qualitative interviews) will

---

be offered. If a participant withdraws or discontinues the study early, they may be replaced at the discretion of the sponsor and Principal Investigator.

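### Section 11.2 does not say which average home adherence rate its random-effect logistic model should report, and has no rule for zero failures. Read as a typical-patient rate, the figure can reverse the 75% feasibility conclusion.

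*Combined protocol and SAP*

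**What the plan says.** Adherence is a secondary endpoint scored dose by dose. Section 2.2.2 states: "Adherence will be measured for each dose given and failure would occur if the participant needs to go to the infusion center for administration", whatever the reason. The same item sets the trial's only numeric feasibility threshold: "adherence rates over 75% would be needed to meet criteria for feasibility". It does not say whether the estimate or the lower confidence limit must exceed 75%.

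The data are small. The Study Summary states "The sample size will be 20 participants", and each participant has two infusion-center cycles "followed by 4 cycles at home".

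In section 11.2 the per-dose outcome is "analyzed in repeated measures logistic regression model with a random effect of patient". A term for site of care is included as well, worded as "the fixed effect of the delivery mode (home vs. infusion center"). On what is to be reported, the section says: "The model will be used to compute the average rate of home setting adherence with the corresponding 95% confidence interval". It names no alternative for a fit without failures or without convergence, and does not define the average rate.

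Section 4.4.2 adds: "Participants who withdraw or discontinue the study intervention early will continue to receive their treatment in the infusion center". It also allows such participants to be replaced. No section says whether their later center doses count as home failures or leave the denominator.

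**The concern.** In a logistic model with a random patient effect, two different quantities can be called the average rate. One is the inverse logit of the intercept, the rate for a patient whose random effect is zero. The other integrates over patients and gives the population-average rate. They are close when patients differ little and far apart when most patients succeed every time and a few mostly fail.

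That second pattern is plausible here. If a participant who leaves home dosing is scored as failing each remaining home dose, failures come in runs within a patient. The patient variance is then estimated as very large, the intercept moves up with it, and the typical-patient rate approaches 100% whatever the observed proportion.

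Separately, a program in which every home dose succeeds leaves the model without a finite intercept, so the planned interval does not exist.

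At stake is the figure compared with 75%. A substitute chosen after the data are seen is also open to choice: treating 80 doses as independent gives a much tighter interval than treating 20 patients as the units.

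**Working it through.** **Inputs.** 20 patients and 4 home doses each (Study Summary); binary outcome per dose and the 75% bar (section 2.2.2); random-intercept logistic model (section 11.2). The plan states no expected adherence, clustering or precision for this endpoint, so there is no figure of its own to reproduce. On home doses the delivery-mode term is constant, so the fits below use an intercept only.

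**Model.** logit(p_i) = b + u_i, with u_i ~ N(0, s²).
- Typical-patient rate: 1/(1 + exp(−b)).
- Marginal rate: the average of 1/(1 + exp(−(b + u))) over u.

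Fits are by maximum likelihood with numerical integration over u, and Wald 95% intervals.

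**1. No failures (80/80).** The likelihood increases as b goes to infinity, so there is no finite estimate or Wald interval. With independent doses:
- P(80/80) = 0.98^80 = 0.20 at 98% true adherence.
- P(80/80) = 0.99^80 = 0.45 at 99%.
- At true rates of 75% to 90%, with a patient SD of up to 3 logits, it is below 1%.

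Exact lower limits are 0.025^(1/80) = 95.5% if doses are independent and 0.025^(1/20) = 83.2% with the patient as the unit. Both exceed 75%.

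**2. Clustered failures, observed rate below the bar.** Take 13 patients at 4/4, four at 0/4, and one each at 1/4, 2/4 and 3/4.
- Observed: (52 + 0 + 1 + 2 + 3)/80 = 58/80 = 72.5%.
- Fit: b = 4.92 (SE 3.24), s = 7.95.
- Typical-patient rate: 1/(1 + exp(−4.92)) = 99.3%. Interval on the logit scale: 4.92 ± 1.96 × 3.24 = −1.43 to 11.27, that is 19% to 100%.
- Marginal rate from the same fit: 72.7%.
- Patient as cluster: the SD of the 20 patient proportions is √[(13.875 − 20 × 0.725²)/19] = 0.421; SE = 0.421/√20 = 0.094; 72.5% ± 2.093 × 9.4% gives 52.8% to 92.2%.

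The typical-patient figure passes the bar. The observed and marginal figures do not.

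**3. All-or-nothing patients.** Take 18 patients at 4/4 and two at 0/4, observed 72/80 = 90%. No patient has a mixed outcome, so b and s run to their bounds. The typical-patient rate is about 100% with interval 0 to 1. The marginal rate is still about 90%.

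**4. How often, under assumed permanent return to the center.** Suppose a fixed share of remaining patients leaves home dosing for good at each cycle and all their later doses count as failures. In 300 simulated trials per setting:

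| Leave per cycle | True home rate | Zero failures | Typical-patient interval wider than 50 points | Marginal interval wider than 50 points |
|---|---|---|---|---|
| 2% | 95% | 20% | 57% | 0% |
| 5% | 88% | 1% | 49% | 0% |
| 10% | 77% | 0% | 44% | 0% |

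The last two columns count only trials with at least one failure, as a share of all trials. With normally distributed patient effects, true rates of 75% to 97.5% and no permanent return, the typical-patient interval is that wide in 0–3% of trials at SD 1, 4–13% at SD 2 and 11–26% at SD 3.

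**5. Effect on the verdict.** At 10% leaving per cycle the true rate is (0.9 + 0.81 + 0.729 + 0.6561)/4 = 77.4%. In 600 simulated trials about 40% had observed adherence of 75% or less. In nearly all of these (about 38% of all trials) the typical-patient rate still exceeded 75%. The true rate in this setting is just above the bar, so the reversal is relative to the observed rate.

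**The case against.** The strongest reply is that an average rate most naturally means the population average, and on that reading the model works. This stands. Once there is at least one failure, the marginal rate stays near the observed proportion (about 90% and 72.7% in the two examples), and its interval was never wider than 50 points in the simulations. The trouble is that section 11.2 does not choose this reading, and the inverse logit of the intercept is equally compatible with its text.

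Three stronger inferences are tempting, and the documents do not support them.
- A reader might infer that clustering breaks the model whichever average is used. It does not, for the reason just given.
- A reader might infer that any clustering sends the patient variance to infinity. That needs every patient to be all-success or all-failure, which has probability of at most about 2% for a patient SD of up to 3 logits. Seventeen patients at 4/4 with others at 0/4, 1/4 and 1/4 give a finite SD of 8.1.
- A reader might infer that 80/80 leaves feasibility undecided. Both exact lower limits exceed 75%; only the planned interval is missing.

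It is also fair to say that section 4.4.2 does not make clustering certain. It concerns withdrawal and discontinuation, allows replacement, and leaves open whether later center doses count. With little or no clustering and true adherence of about 80% to 95%, the planned fit is mostly usable.

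**Conclusion.** The point holds in a limited form. Section 11.2 takes the figure compared with 75% from a model that can give a misleading rate under the typical-patient reading and no interval when no dose fails, and it neither defines the average nor names a fallback. The possible error is large: 99.3% against 72.5% observed in one plausible data set, on opposite sides of the bar. How often it would matter depends on how strongly failures cluster and on whether center doses after leaving home dosing count as failures; neither is given. It would be wrong to conclude that the adherence rate often cannot be produced at all, because the marginal rate can be computed whenever there is a failure and the bar is clearly met when there is none. Adherence is a secondary endpoint of a 20-patient pilot, but it is the only one with a numeric feasibility threshold and the correction costs almost nothing, so the change should be made.

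**What to change.** In section 11.2, replace the model as the source of the feasibility figure, for example:

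*Home adherence is the number of successful home doses divided by the number of home doses in the denominator, pooled over patients. Its 95% confidence interval treats the patient as the cluster (cluster bootstrap or cluster-robust). If there are no failures, an exact binomial interval with the patient as the unit is used. This rate is compared with 75%. The random-effect logistic model is a sensitivity analysis and reports the marginal rate.*

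The text should also state whether scheduled home doses given at the center after withdrawal or discontinuation count as failures, how replaced participants enter the denominator, and whether the estimate or the lower limit must exceed 75%. With 20 patients the zero-failure rule gives a lower limit of 83.2%.

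The cost is a few sentences and no new data. The downside is that, with 20 clusters, the interval may be wide or slightly off nominal coverage. A plain symmetric interval can also pass 100%: for 18 patients at 4/4 and two at 0/4, SE = √(20 × 0.09/19)/√20 = 0.069, and 90% ± 2.093 × 6.9% runs from about 75.6% to 104.4%. The bootstrap or a logit scale avoids this.
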